5.1.3 Enrolment

After signing the informed consent/assent form, if an individual is determined to be eligible for study participation, the investigator or delegate will enroll the subject and enter the subject information and stratification information into the Electronic Data Capture system (EDC). The EDC system is integrated with interactive response technology (IRT) system for randomization.

5.1.4 Randomization

Enrolled subjects will be assigned a unique Subject ID manually entered in EDC. Subject information and stratification information (ie, age) are automatically transferred to the IRT system for randomization in a 1:1:1:1:1:1 ratio into 6 treatment groups and automatically assigned a unique pack ID. The subject ID will be the subject's unique identification number for all eCRFs and associated study documentation that will be used for duration of the study. After randomization, the screening number ceases to be used and remains in the screening and enrolment log only. The list of randomization assignments is produced by the IRT service provider and approved by the sponsor or delegate prior to study start.

Randomization will be stratified by age (cohorts of 6 months through <36 months, and 3 years through <9 years) and by site. The age cohorts will be of equal size. Once an age cohort attains its planned size (ie, half of the planned study sample size) the randomization in this age cohort will be blocked.

If for any reason, after signing the ICF/assent, the subject who is eligible and enrolled fails to be randomized, this is called a randomization failure. The reason for all randomization failures should be recorded in the screening and enrolment log and in the source document as specified in the source data agreement (SDA). The information on

subjects who are randomization failures should be kept distinct from subjects who are screen failures, as described in [section 5.1.2, Screening](#).

If for any reason, after randomization the subject fails to undergo treatment, this is an early termination and the reason should be recorded in source document as specified in the SDA. The information on these early termination subjects should be kept distinct in the source documentation from randomization failures.

5.1.5 Blood draw

The baseline blood draw must be performed after obtaining informed consent, but prior to randomization. Note: if a baseline blood sample is not obtained, the subject is not eligible for the study. The following volumes of blood will be withdrawn: approximately 6 mL per blood draw for subjects. Details regarding the volume of blood and testing to be performed are in [section 3.5, Collection of Clinical Specimens](#). These data will be written in the source document (see [Section 9.1, Source Documentation](#)) and must be documented in the eCRF.

A topical analgesic/anesthetic/icepack may be used for the blood draw. However, the topical analgesic/anesthetic/icepack used for the blood draw should not be applied to the area of vaccination.

In the exceptional situation in which a clinic visit is not possible, such as in the case when a site is not able to see study subjects at the clinic due to local regulations related to the coronavirus pandemic, a home visit (only at Day 43 or 202) may be considered. The site must get approval from the sponsor to conduct home visits. The site must also have sponsored approved Standard Operating Procedures/Instructions for conducting home visits and the collection of blood samples in the home setting, prior to the home visit occurring. These procedures may also need to be approved by the site's IRB/EC depending on local and country regulations.

5.2 Vaccination Clinic Visit(s)

Vaccination will be performed on Day 1, and Day 22.

Ensure the Day 1 and Day 22 blood samples are taken **prior** to each vaccination.

After completing the pre-vaccination procedures on Day 1, administer the vaccine to the subject according to the procedures described in [section 6.3, Vaccine Preparation and Administration](#). Observe the blinding procedures described in [section 3.3, Blinding Procedures](#).

Prior to administration of the second vaccination at Day 22 confirm that the subject is eligible for additional study vaccinations and does not meet any criteria for delaying additional or stopping study vaccinations as described in [section 4, Selection of Study Population](#).

5.2.1 Post-vaccination Procedures

The following post-vaccination procedures will be performed on Day 1 and Day 22.

After vaccination, the subject will be observed for at least 30 minutes including observation for unsolicited adverse events, solicited adverse events, and body temperature measurement. Record all safety data collected during this time in the subject's source document and eCRF.

A Subject Diary Card will be used in this study to document solicited adverse events. The Subject Diary Card is the only source for collection of these data; therefore, it is critical that the parent(s)/LAR(s) completes the Subject Diary Card correctly. The parent(s)/LAR(s) should be trained on how and when to complete each field of the Subject Diary Card.

The parent(s)/LAR(s) should be trained on how to self-measure local solicited adverse events and body temperature. The measurement of solicited local adverse events is to be performed using the ruler provided by the site.

The parent(s)/LAR(s) should be instructed how to perform body temperature measurement using the thermometer provided by the site. If the subject feels unusually hot or cold during the day, the parent(s)/LAR(s) should check body temperature. If the subject has fever, the highest body temperature observed that day should be recorded in the Subject Diary Card.

Subject Diary Card training should be directed at the individual(s) who will perform the measurements of adverse events and who will enter the information into the Subject Diary Card. This individual may not be the parent(s)/LAR(s), but if a person other than the parent(s)/LAR(s) enters information into the Subject Diary Card, this person's identity must be documented in the Subject Diary Card and subject's source record. Any individual that makes entries into the Subject Diary Card must receive training on completion of the Subject Diary Card prior to entering data at visit 1 (Day 1) and visit 2 (Day 22). This training must be documented in the subject's source record.

The same individual (preferably) should complete the Subject Diary Card throughout the course of the study.

The site should schedule the next study activity with the subject's parent(s)/LAR(s). It is recommended for the site to already schedule in advance the remaining upcoming study activities.

The subject's parent(s)/LAR(s) should be reminded of the next planned study activity. The parent(s)/LAR(s) will be reminded to complete the Subject Diary Card and to contact the site if there are any questions, and to contact the site immediately (or as soon as the subject is medically stable) if the subject has a medical condition that leads to a hospitalization or an emergency room visit or to a visit to/by a doctor or is of concern.

5.2.2 Post-vaccination Reminders

Reminder calls or alerts are not intended to be an interview for collection of safety data. If the subject's parent(s)/LAR (s) wishes to describe safety information, this information should only be collected by a trained health care professional at the site, and the safety data described must be written down in the subject's medical chart.

Subject Diary Reminder Calls

Subject Diary Card reminder calls will be performed on Day 5, and on Day 26. The purpose of this call is to remind the subject's parent(s)/LAR(s) about completion of the Subject Diary Card. The call follows the Subject Diary Card reminder telephone call script provided to the site. The subject's parent(s)/LAR(s) should be reminded to contact the site via the telephone number provided in the informed consent to discuss medical questions.

5.3 Post-vaccination Visit(s)

Post-vaccination clinic visits will be performed on Day 22, Day 43, and Day 202.

5.3.1 Follow-up Clinic Visit(s)

Safety follow-up clinic visits will be performed on Day 22, Day 43, and Day 202.

During the follow-up clinic visit 2 and 5 (Days 22 and 43), the Subject Diary Card⁸ will be reviewed. No changes to the information recorded within the Subject Diary Card are permissible. For details on the Subject Diary Card see [sections 3.4.2, Tools Used for Data Collection](#) and [5.2.1, Post-vaccination Procedures](#). The parent(s)/LAR (s) will be interviewed to determine if any unsolicited adverse events occurred and if any associated

⁸ In case a clinic visit is not possible, subjects should be instructed on how to return the Subject's Diary Card.

concomitant medications or vaccines were taken/ received in the time since the last clinic visit. This interview will follow a script which will facilitate the collection of relevant safety information. The qualified health care professional reviewing these data will discuss the symptoms (if any) reported by the subject's parent(s)/LAR(s) and will determine if any additional diagnoses and/or adverse events are present. All adverse events reported by the parent(s)/LAR(s) at the follow-up clinic visits on Day 22 and Day 43 must be recorded in the subject's source document and on an Adverse Events eCRF, as specified in [section 7.1, Safety Assessment](#), and not written on the script used for the interview. During the Day 202 safety follow-up clinic visit, only the following subset of unsolicited AEs and the associated concomitant medications/vaccinations will be documented in the subject's eCRFs: all SAEs, NOCDs, AEs leading to vaccine and/or study withdrawal, and AESIs.

Perform a brief symptom-directed physical examination if necessary according to symptoms the subject has reported. This is a physical examination that will include an examination of organ systems that are relevant to the investigator based on review of the subject's reported adverse events and concomitant medication use. The physical assessment must be performed by the investigator or designee of the investigator, who is qualified to perform a physical assessment in accordance with their institutional policy. Corresponding information is documented in the subject's source document and eCRF(s).

The site should schedule the next study activity: safety call with the subject's parent(s)/LAR(s). The subject's parent(s)/LAR(s) will receive a written reminder of the next planned study activity. The subject's parent(s)/LAR(s) will be reminded to contact the site if there are any questions and to contact the site immediately (or as soon as the subject is medically stable) if the subject has a medical condition that leads to a hospitalization or an emergency room visit.

5.3.2 Safety Follow-up Calls

Safety follow-up calls will be performed on Days 92, 152 and 387.

Safety follow-up calls are calls made to the subject by a qualified health care professional designated on the site's roles and responsibilities log. These calls will follow a script which will facilitate the collection of relevant safety information. The subject's parent(s)/LAR (s) will be interviewed according to the script, and information relating to the following unsolicited adverse events: SAEs, AESIs, AEs leading to withdrawal, and/or NOCD and associated concomitant medications or vaccinations. All safety information described by the subject must be written down in a designated location within the source document and not written on the script used for the telephone call.

The site should schedule the next study activity: clinic visit or safety call with the subject's parent(s)/LAR(s).

The parent(s)/LAR(s) will be reminded to contact the site if there are any questions and to contact the site immediately (or as soon as the subject is medically stable) if the subject has a medical condition that leads to a hospitalization or an emergency room visit.

5.4 Unscheduled Visits

An unscheduled visit describes a non-routine study visit triggered by a specific event. These could include anticipated or unanticipated adverse events or interventions.

Unscheduled visits may include, but are not limited to, review of Subject Diary Card data, review of systems, symptom directed physical examination, and blood sampling for safety, and should be documented in the subject's source documentation.

5.5 Study Termination Visit

The study termination visit (ie, safety phone call) will occur on Day 387. The date of termination is the date of the last contact (clinic visit or telephone call) in which the subject's health status was assessed or, in cases where the subject does not agree to any further safety follow-up, it is the date consent is withdrawn. This date should be recorded on the termination eCRF page. For visit procedures to be performed for a subject whose planned study participation ends prematurely, please see [section 5.5.1, Early Termination Visit](#).

During the telephone call, the following procedures will be performed if applicable: review of Subject Diary Card, collection of Subject Diary Card, review of systems, interview of the subject's parent(s)/LAR (s) to collect unsolicited AEs, AEs leading to withdrawal, SAEs, AESIs, and NOCD, interview of subject and/or parent(s)/LAR (s) to collect associated concomitant medications/ vaccinations, symptom-directed physical assessment, and blood sampling for immunogenicity.

The site will review with the subject's parent(s)/LAR(s) the plan of when information relating to the subject's participation in the study may be available (eg, study results, treatment assignments). It will also be discussed how information relating to the subject's participation in the study will be shared with the subject's health care provider, if the subject's parent(s)/LAR(s) chooses to share this information.

The site will complete the termination eCRF page and this will mark the completion of the subject's participation in the study.

5.5.1 Early Termination Visit

When a subject is withdrawn from treatment or withdraws from the study, the investigator will notify the sponsor or delegate and, when possible, will perform the procedures listed below. The reason(s) for the early termination will be included in the subject's source

documentation. If the early termination visit is a telephone call, collect as much information as possible. Early termination visits include subjects who were randomized but not treated.

At the clinic visit or during the telephone call, the following procedures will be performed as during the study termination visit, see [section 5.5 Study Termination Visit](#), if possible.

In addition, the following procedures will be performed:

- Collect and review Subject Diary Card, if applicable.⁹
- Review the subject's safety data (if collection of these was in progress at the time of study completion).

The site will review with the subject's parent(s)/LAR (s) the plan of when information relating to the subject's participation in the study may be available (eg, study results, treatment assignments). It will also be discussed how information relating to the subject's participation in the study will be shared with the subject's health care provider, if the subject's parent(s)/LAR(s) chooses to share this information.

The site will complete the termination eCRF page and this will mark the completion of the subject's participation in the study.

⁹ In case a clinic visit is not possible, subjects should be instructed on how to return the Subject's Diary Card.

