9. Any other clinical condition that, in the opinion of the investigator, might interfere with the results of the study or pose additional risk to the subject due to participation in the study.

10. Individuals who received any other vaccines within 14 days (for inactivated vaccines) or 28 days (for live vaccines) prior to enrolment in this study or who are planning to receive any vaccine prior to day 43. Following day 43 other vaccines may be administered, including seasonal flu.

Prior to receipt of the second vaccination, subjects must be re-evaluated to confirm that they are eligible for subsequent vaccination. If subjects meet any of the original exclusion

criteria listed above, they should not receive the second vaccination. These subjects will be requested to fulfill all the scheduled clinic visits and calls for safety follow-up. No further blood samples will have to be taken. This review of eligibility should be documented in the source document and the reason for not administrating a scheduled study vaccine should be documented in the eCRF.

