4.4 Criteria for Repeat Vaccination in the Study

Prior to receipt of the second study vaccination, subjects must be evaluated to confirm that they are eligible for subsequent vaccination. If subjects meet any of the criteria listed below, they should not receive additional vaccinations.

- Has experienced any immediate allergic reaction after the previous study vaccination
- Has experienced any serious adverse event judged to be possibly or probably related to study vaccination, including hypersensitivity reactions.
- Has developed any clinically significant medical condition which, in the opinion of the investigator, may pose additional risk to the subject if he/she continues to participate in the study.

Subjects who meet any of these criteria must not receive further study vaccinations. However, the subject's parent(s)/LAR(s) should be encouraged to continue study participation of the subject.

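### Section 5.5.1 makes stopping vaccination a trigger for early termination, against sections 4.2 and 4.4, so a child who only misses dose 2 could lose safety follow-up from about Day 22

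*Protocol*

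**What the plan says.** **Section 5.5.1 (Early Termination Visit).** The trigger is "When a subject is withdrawn from treatment or withdraws from the study, the investigator will notify the sponsor or delegate". The sentence goes on to require the early termination procedures where possible. A separate sentence adds that "Early termination visits include subjects who were randomized but not treated". The section ends with "The site will complete the termination eCRF page and this will mark the completion of the" subject's participation.

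**Section 4.2.** This covers a child who, on re-evaluation before dose 2, meets an exclusion criterion and so is not vaccinated again: "These subjects will be requested to fulfill all the scheduled clinic visits and calls for safety follow-up". It adds: "No further blood samples will have to be taken".

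**Section 4.4.** This lists further reasons to withhold dose 2. They include "Has experienced any immediate allergic reaction after the previous study vaccination" and a serious adverse event judged related to vaccination. For these children the parents "should be encouraged to continue study participation of the subject".

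**Section 5.1.4.** For a child who is randomized but never vaccinated: "If for any reason, after randomization the subject fails to undergo treatment, this is an early termination".

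**References to 5.5.1.** Section 3.8, section 5.5 and note n to Table 2 send the reader to the early termination visit only when a child leaves the study or ends participation early.

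**The concern.** Section 5.5.1 treats two different events as one. Stopping vaccination is a decision about the intervention; leaving the study is a decision about follow-up. By attaching the termination page to both, the section tells a site to close a child whom 4.2 and 4.4 want kept.

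What is at stake is late safety. One of the primary safety endpoints in section 8.1.1.1 is the percentage of children with SAEs, AESIs, new-onset chronic disease, or an AE that ended vaccination or participation, over Days 1 to 387. The children exposed to the faulty rule include those stopped after an immediate allergic reaction or a related serious event following dose 1. These are the children whose later course is of most clinical interest.

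**Working it through.** **The instructions side by side, for a child barred from dose 2 at Visit 2**

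| Section | Instruction for this child |
|---|---|
| 4.2 | Asked to attend all remaining visits and calls for safety; no more blood samples |
| 4.4 | Parents encouraged to keep the child in the study |
| 3.8, 5.5, Table 2 note n | Early termination applies to leaving the study, so not to this child |
| 5.5.1 | Withdrawn from treatment, so early termination; the termination page ends participation |

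The conflict with 4.2 is direct. With 4.4, which only encourages, 5.5.1 works against the intention.

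Three readings might rescue 5.5.1, and none does:

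- *The trigger means only never-treated children.* Those children have their own sentence in 5.5.1 and their own rule in 5.1.4. Nothing limits the trigger to them.
- *Section 3.8 already secures safety follow-up.* Its text on continuing for safety concerns a parent who wants to withdraw the child. It does not concern an investigator who withholds dose 2.
- *The rule in 5.5 on the termination date keeps the child open.* It says which date to record. It does not say that a child stopped only from vaccination remains in follow-up.

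**Follow-up lost per child closed at Visit 2**

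Inputs from Table 2: Visit 2 is V1 + 21 days, window -1 to +7, so nominally Day 22 and in practice Day 21 to Day 29. Visit 7 is V2 + 365 days, window -7 to +7.

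Reproducing the plan's end of follow-up: 22 + 365 = Day 387, as stated in section 5.5.

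- Nominal loss: 387 - 22 = 365 days; 365/387 = 94.3%. Counting elapsed days from Day 1 (386) gives 365/386 = 94.6%.
- Days lost across the windows: 365 - 7 = 358 to 365 + 7 = 372.
- Smallest share: Visit 2 on Day 29, Visit 7 on Day 29 + 358 = 387; 358/387 = 92.5%.
- Largest share: Visit 2 on Day 21, Visit 7 on Day 21 + 372 = 393; 372/393 = 94.7%.

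**Assessments lost**

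Table 2 schedules assessment of SAEs, AESIs and new-onset chronic disease at Visits 1 to 7, which is 7 occasions. Closure at Visit 2 omits two clinic visits (V3, Day 43; V6, Day 202) and three calls (V4, Day 92; V5, Day 152; V7, Day 387): 2 + 3 = 5 of 7.

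**What is not lost**

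The 7-day solicited and 21-day unsolicited periods after dose 1 are essentially complete by Visit 2. Section 4.2 asks for no further blood, so no planned serology is at stake for the children it covers. An AE that stopped vaccination is already counted in the endpoint as leading to vaccine withdrawal.

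**The case against.** The best defence is that 5.5.1 is general text and must give way to the specific rule. A site deciding about dose 2 is sent by section 5.2 to section 4, where it meets the instruction to keep the child. Section 4.2 also has the site record in the eCRF why the dose was not given, so a missed dose can be documented without closing the child. Section 8.4.1.1, section 8.4.2.1.3 and SAP 13.3 all separate withdrawal from vaccination from withdrawal from the study. Section 7.1.3 requires every AE to be followed until it resolves or is judged chronic or stable, so the event that stopped vaccination is followed under any reading. Finally, 5.5.1 sets no time for the termination page, and section 5.5 dates termination by the last contact at which health was assessed. On that view a site could notify the sponsor at Visit 2, continue the calls, and complete the page at the last one.

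Much of this stands. It shows that 5.5.1 is a drafting slip rather than an intended policy, and it makes a wrong closure less likely. SAP 9.1 also summarizes observation time by vaccine group, which would expose shortened follow-up, although it could not recover the missing data.

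The last argument is strained. The page is a step of the early termination visit itself, and the qualifier on feasibility attaches to the procedures, not to the sentence about the page. The protocol states no order of precedence between 4.2 and 5.5.1, and 5.5.1 is the section a site would open when completing that form. Following the AE that stopped vaccination does not capture a new SAE, AESI or chronic disease arising later.

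**Conclusion.** The concern holds; it is minor, with high confidence. Section 5.5.1 states a rule that conflicts directly with 4.2, works against 4.4, and is broader than the scope that 3.8, 5.5 and Table 2 note n give it.

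The per-child figures assume that a site closes the child at Visit 2 despite the contrary text. The documents give no rate of missed second doses; the 14% in section 8.5 is exclusion from analysis, not missed doses. No effect on the percentages by vaccine group is therefore claimed, and none is claimed on immunogenicity or early reactogenicity.

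**What to change.** Amend section 5.5.1 only.

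1. Replace the opening condition so that the procedure applies when a child leaves, or is removed from, the study, including a child randomized but never vaccinated. Leave the rest of that sentence as it is.
2. Add, in substance: *Stopping further vaccination is not in itself an early termination. The sponsor or delegate is informed, the child is asked to stay in the study to Day 387 under section 4.2 or 4.4, and the termination page is completed only at Day 387 or when the child actually leaves the study.*

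This keeps the rule in 5.1.4 for children who are never vaccinated and does not change who receives dose 2.

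The cost is a wording amendment to one section, with sponsor and IRB/EC approval and health authority approval where required (section 13.4), plus a reminder to sites. The visits and calls are already scheduled for these children, so no procedure is added.
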